**Proprietary confidential information.**

© 2015 Boehringer Ingelheim International GmbH or one or more of its affiliated companies. All rights reserved.

This document may not - in full or in part - be passed on, reproduced, published or otherwise used without prior written permission.

Table 7.6: 1 Sample size estimations for annualised rate of moderate to severe COPD exacerbation under different dispersion parameters with 2-sided type I error rate of 0.01, 90% power, annual rate of 0.85 in Tio 5 and rate ratio = 0.88

Annual Rate in Tio 5 (r 1 )	Annual Rate in T+O FDC (r 2 )	r 2 /r 1	Dispersion Parameter	N per arm	Average exposure (months)	Total exposure adjusted for 15% loss of information (patient – years)	Power (after adjusting 15% loss of information in patient-years)
0.85	0.748	0.88	0.625 (SPARK)	3427	12	2913	85.8%
0.85	0.748	0.88	0.7	3563	12	3029	86.0%
0.85	0.748	0.88	0.8	3745	12	3184	86.2%
0.85	0.748	0.88	0.9	3927	12	3338	86.4%

The above calculation is based on the formulas in Zhu and Lakkis [P14-09564] and was calculated using the validated software package R. A sample size of 3900 patients per arm will give a power between 90% to 94% under different dispersion parameters to detect a rate ratio of 0.88 between T+O FDC and Tio 5 in the annualised rate of moderate to severe COPD exacerbation assuming the annual rate in Tio 5 is 0.85 and two-sided type I error rate of 0.01. After adjusting for a 15% loss of information in patient-years and the same assumptions as above, a sample size of 3900 patients per arm will give a power between 86.1% to 90.6%

Assuming the proportion of patients who had at least one moderate to severe COPD exacerbation within 1 year in the Tio 5 arm is 0.65, a hazard ratio between T+O FDC and Tio 5 of 0.88, a two-sided type I error rate of 0.01 and power of 90%, the estimated sample size for time to the first moderate/severe COPD exacerbation is 2915 patients per arm (using nQuery Advisor 7.0). A sample size of 3900 patients per arm will give a power of 97% using the same assumptions.

A sample size of 3900 patients per arm or 7800 patients in total is selected for this trial because it provides acceptable power to detect a 12% reduction in annualised rate of moderate to severe COPD exacerbation of T+O FDC as compared with Tio 5 using a two-sided type I error rate of 0.01, under a reasonable range of dispersion parameters of the negative binomial distribution and assuming the annual rate in Tio 5 is 0.85. This sample size also gives sufficient power to detect a 12% reduction in the hazard rate of moderate to severe COPD exacerbation of T+O FDC as compared to Tio 5 at a two-sided type I error rate of 0.01 and assuming the proportion of patients who had at least one moderate/severe COPD exacerbation after 1 year in the Tio 5 arm is 0.65.

Proprietary confidential information.

© 2015 Boehringer Ingelheim International GmbH or one or more of its affiliated companies. All rights reserved.

This document may not - in full or in part - be passed on, reproduced, published or otherwise used without prior written permission.

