**Proprietary confidential information.**

© 2015 Boehringer Ingelheim International GmbH or one or more of its affiliated companies. All rights reserved.

This document may not - in full or in part - be passed on, reproduced, published or otherwise used without prior written permission.

as well as the logarithm of the treatment exposure as an offset. In all analyses of annualised rate of event, the length of the event will be subtracted from the extent of exposure or the length of the observation period because one cannot expect to have another event during an event. Moderate to severe COPD exacerbations occurring within 1 day (i.e.: 24 hours) after the last drug administration date are included in the primary analysis.

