## 7.6 DETERMINATION OF SAMPLE SIZE

Based on a recent publication on the SPARK study (Wedzicha, et al, Lancet, 2013) and data from a previous BI study [REDACTED], the rate ratio and hazard ratio of moderate to severe COPD exacerbation between T+O FDCs and Tio 5 are assumed to be 0.88.

Assuming an annualised rate of moderate to severe COPD exacerbation for Tio 5 to be 0.85, a 12-month fixed study duration, two-sided type I error rate of 0.01 and 90% power, the sample size depends on the dispersion parameter for the negative binomial distribution. [Table 7.6: 1](#) gives the sample size estimations for a range of the dispersion parameters. In addition, assuming a 15% loss of information in patient-years, the estimated power corresponding to the sample size is also provided in the last column in Table 7.6: 1 below.

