## 6. GENERAL ANALYSIS DEFINITIONS

### 6.1 TREATMENTS

As described in Section 4 of the revised CTP, patients will be randomized in equal allocation to one of two treatment groups delivered by the Respimat® inhaler:

- Tiotropium + olodaterol fixed dose combination (FDC) (5µg / 5µg) inhalation solution once daily
- Tiotropium (5 µg) inhalation solution once daily.

Table 6.1: 1 Treatments and their labels

Treatment	Short label
Tiotropium + olodaterol FDC (5 µg / 5 µg) inhalation solution	T+O 5/5
Tiotropium (5 µg) inhalation solution	Tio 5

The trial consists of a 360 days of treatment followed by a 21 day residual effect period.

For analysis purposes the following periods are defined:

- Planned study period  
The planned study period is defined as 360 days of treatment + 21 days of follow up after the administration of the first dose of trial medication according to the CTP flow chart.
- Planned treatment period  
The planned treatment phase is defined as 360 days of treatment + 1 day for wash-out according to the CTP flow chart.
- Actual treatment period  
The actual treatment period is defined as the interval from first in-take of study medication until 1 day after last in-take of study medication.
- On-treatment period  
The on-treatment period is defined as the interval from first in-take of study medication until 21 days after last in-take of study medication.

Patients that discontinue early will be monitored for exacerbations and vital status until they have reached the end of their planned study period.

Table 6.1:2 Analyses performed within each period

Types of Analyses to be performed	Periods			
	Actual treatment period (Treatment +1 day wash-out)	Planned treatment period (includes 1 day wash-out)	Planned study period (includes residual effect period of 21 days)	On-treatment period (includes residual effect period of 21 days after last drug intake)
Primary Exacerbation analysis	✓			
Sensitivity primary exacerbation analysis		✓		
Key secondary exacerbation analysis	✓			
AE safety analysis				✓

Patients will be analyzed according to the treatment group of the first treatment received. Potential treatment switcher scenarios caused by treatment misallocation will be discussed at the Blinded Report Planning Meeting (BRPM). After database lock (DBL) patients who fall into these discussed scenarios will be analyzed according to meeting decisions.

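### The post-loss power of 86.1% to 90.6% in Protocol 7.6 requires every patient to have exactly 0.85 year at risk; the same 15% loss under assumed gradual dropout gives about 84.6% to 89.6%

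*Protocol*

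**What the plan says.** Protocol 7.6 takes a control rate from "Assuming an annualised rate of moderate to severe COPD exacerbation for Tio 5 to be 0.85", a rate ratio and hazard ratio that "are assumed to be 0.88", and "a 12-month fixed study duration". The design target is a "two-sided type I error rate of 0.01 and 90% power". Table 7.6:1 lists four dispersion values (0.625, 0.7, 0.8, 0.9). For each it gives N per arm at full follow-up, a column headed "Total exposure adjusted for 15% loss of information (patient"-years), and the power after that loss. For the chosen size the text adds that "a sample size of 3900 patients per arm will give a power between 86.1% to 90.6" percent. The section does not say what the 15% consists of or how it is spread over patients.

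Protocol 7.3.1 and SAP 7.4 define the primary analysis as a negative binomial model with log treatment exposure as offset, counting events up to one day after the last dose. Protocol 7.3.1 and SAP 6.9 add that "the length of the event will be subtracted from the extent of exposure". SAP 6.1 describes the length as follows: "The trial consists of a 360 days of treatment followed by a 21 day residual effect period".

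**The concern.** A total of patient-years does not fix the power of a negative binomial comparison; the spread of those years over patients matters as well. With overdispersion, each extra month in the same patient adds less information than the month before. A planner who gives everyone the mean follow-up therefore credits the trial with the most information that the total can carry.

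The planned analysis cannot have equal exposure. Patients who stop early are still followed for exacerbations, but their later events fall outside the primary counting window, so their exposure is short while completers have about a full year.

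Protocol 7.6 rests the choice of 7800 patients on acceptable power, and 86.1% to 90.6% is its only rate-endpoint power at 3900 per arm that allows for any loss. What is at stake is the accuracy of that figure.

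**Working it through.** **Inputs (Protocol 7.6).** r1 = 0.85; r2 = 0.85 × 0.88 = 0.748; |ln 0.88| = 0.12783; two-sided alpha 0.01, so z = 2.5758; n = 3900 per arm; dispersion k from 0.625 to 0.9; mean exposure 1 − 0.15 = 0.85 year.

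**Formula.** Information per patient in an arm is I = E[r·t/(1 + k·r·t)], averaged over follow-up t. With V = 1/I1 + 1/I2, power = Φ(0.12783·√(n/V) − 2.5758). If t is the same for everyone, V = (1/r1 + 1/r2)/t + 2k, where 1/r1 + 1/r2 = 2.5134. This is the unpooled form of the cited negative binomial method.

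**Step 1: reproduce the plan.**
- At t = 1 and 90% power, N per arm is 3427, 3564, 3746 and 3928, against 3427, 3563, 3745 and 3927 stated; the differences are rounding.
- The exposure column is N × 0.85 (for example 3427 × 0.85 = 2913). It fixes the total, not the spread.
- With t = 0.85 for every patient, the four table powers are 85.8%, 86.0%, 86.2% and 86.4%, as printed.
- At n = 3900 and k = 0.9: V = 2.5134/0.85 + 1.8 = 4.7569, and power = Φ(3.6603 − 2.5758) = Φ(1.0845) = 86.1%.
- At n = 3900 and k = 0.625: V = 2.9569 + 1.25 = 4.2069, and power = Φ(1.3164) = 90.6%.
- Reading the loss as 15% fewer patients with full follow-up gives about 83.7% in every row, which does not match.

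**Step 2: direction.** r·t/(1 + k·r·t) is strictly concave in t. For a fixed mean of 0.85 year in both arms, E[I] is largest when all t are equal, and any spread lowers it. The direction needs no assumption about the dropout pattern; the size does.

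**Step 3: size under an assumed pattern.** For exponential dropout truncated at one year, (1 − e^−h)/h = 0.85 gives h = 0.334, so 1 − e^−0.334 = 28% stop early.
- k = 0.9: V = 4.9266; power = Φ(1.0209) = 84.6%.
- k = 0.625: V = 4.3301; power = Φ(1.2606) = 89.6%.

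**Step 4: limiting case.** If 15% contribute nothing and 85% a full year, V = (2.5134 + 2k)/0.85.
- k = 0.9: V = 5.0746; power = 83.3%.
- k = 0.625: V = 4.4275; power = 88.8%.

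| Spread of the same 15% loss, n = 3900 | k = 0.9 | k = 0.625 |
|---|---|---|
| Equal, 0.85 year each (as stated) | 86.1% | 90.6% |
| 30% stop uniformly over the year | 84.7% | 89.7% |
| Exponential dropout | 84.6% | 89.6% |
| 20% stop uniformly in first half-year | 84.3% | 89.4% |
| All loss at day 0 (limit) | 83.3% | 88.8% |

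With each row's own N, exponential dropout turns the last table column into 84.6%, 84.7%, 84.8% and 84.9%.

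**Step 5: simulation.**
- 4000 runs at k = 0.9 gave 86.5% with equal exposure and 85.1% with uneven exposure (Monte Carlo standard error about 0.6 point).
- 800 runs per scenario (standard error about 1.0 to 1.3 points), for k = 0.9 and 0.625, gave 86.5% and 91.0% with equal exposure, 84.8% and 89.8% with uniform dropout, and 82.6% and 88.4% with exponential dropout.

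The direction agrees throughout. The 800-run exponential results lie below the formula by 1.2 to 2.0 points, which is within two standard errors.

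**Step 6: the label.** With equal exposure of 0.85 year, statistical information (1/V) falls by 1 − 4.3134/4.7569 = 9.3% at k = 0.9 and 1 − 3.7634/4.2069 = 10.5% at k = 0.625, not by 15%. A true 15% loss of information gives the limiting-case figures. The phrase in Protocol 7.6 can be read either way.

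**The case against.** The strongest reply is that there is no calculation error. The figures follow exactly from the cited formula, and using mean exposure is a common planning simplification. That stands. The fault is an unstated assumption that the planned analysis cannot meet.

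A second reply is that the shift is small. The protocol's own range spans 4.5 points over dispersion, and lowering the control rate to 0.80 with equal exposure would also give 84.5% at k = 0.9. That stands too, and it is why the sample size is not in question.

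Three stronger readings are tempting, and the documents do not support them.

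- **That subtracted event days and the 360-day period lower power further, to about 83% to 89%.** The 15% is never broken down and may already cover both. No event length is given. If 0.85 is a rate per calendar year, removing event days raises the rate by the factor that shortens exposure, r·t is unchanged, and no information is lost. Visit 6 is at day 360 with a window of up to 7 more days, and SAP 7.7 has an exposure category of 361 days or more. Counting 360/365 as extra would cost 0.3 to 0.4 point.
- **That the stated range is an upper bound on the trial's power.** It is one only if the mean loss is 15% and the other inputs hold. Exponential dropout with an 11% loss gives 86.2% to 90.9%.
- **That the day-0 case describes this trial.** The treated set requires at least one dose, so that case is a mathematical limit and not a plausible pattern.

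**Conclusion.** The point holds, at a modest size. For a 15% mean loss of patient-years, 86.1% to 90.6% requires equal exposure of 0.85 year, which an on-treatment analysis will not have. Under assumed exponential dropout the figure is 84.6% to 89.6%, a shortfall of 1.0 to 1.5 points. The limit is 83.3% to 88.8%.

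These values rest on the protocol's rates, rate ratio and dispersion range, on the same dropout pattern in both arms, and on stopping that is unrelated to a patient's exacerbation risk. The documents supply no pattern, so the exact size is conditional; the direction is not. A reader might infer that 3900 per arm is too few, but nothing here shows that.

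**What to change.** In Protocol 7.6, name the dropout pattern behind the 15%, compute power from patient-level exposure, and restate both the 3900-per-arm sentence and the last column of Table 7.6:1. Under exponential dropout with mean 0.85 year these become about 84.6% to 89.6%, and 84.6% to 84.9% down the column. If another pattern is better supported by earlier trials, use it and say so.

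Add one sentence on what the 15% covers: dropout only, or also event time and the length of the treatment period, and whether it means patient-years or statistical information. State also whether 0.85 is per calendar year or per event-free year.

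If event time is then shown to be extra, give it as a conditional sensitivity calculation. For illustration, an assumed 7 to 28 days per event on top of exponential dropout gives 84.24% down to 83.05% at k = 0.9, and 89.26% down to 88.15% at k = 0.625.

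The cost is a few sentences and one table column, with a slightly less favourable figure. Sample size, analysis and conduct do not change.

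### Section 7.6 powers the key secondary endpoint on a 65% event share in the Tio 5 arm, but the primary calculation's model implies 47–49%; at HR 0.88, power at 3900 per arm is about 88–90%, not 97%

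*Protocol*

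**What the plan says.** All of this is in protocol section 7.6. The effect assumption is shared by both endpoints: "the rate ratio and hazard ratio of moderate to severe COPD exacerbation between T+O FDCs and Tio 5 are assumed to be 0.88".

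- **Primary endpoint.** The calculation begins "Assuming an annualised rate of moderate to severe COPD exacerbation for Tio 5 to be 0.85", over a fixed 12 months, at two-sided alpha 0.01 and 90% power. It uses a negative binomial model with dispersion 0.625, 0.7, 0.8 or 0.9. Table 7.6:1 gives 3427, 3563, 3745 and 3927 per arm. A 15% loss of patient-years is then allowed for: "After adjusting for a 15% loss of information in patient-years and the same assumptions as above", power at 3900 per arm is 86.1% to 90.6%.
- **Key secondary endpoint (time to first event).** The share of patients with "at least one moderate to severe COPD exacerbation within 1 year in the Tio 5 arm is 0.65", the hazard ratio is 0.88, and the design values are "a two-sided type I error rate of 0.01 and power of 90"%. The result is 2915 per arm, followed by "A sample size of 3900 patients per arm will give a power of 97% using the same assumptions". No loss is applied here.
- **Conclusion of the section.** "This sample size also gives sufficient power to detect a 12% reduction in the hazard rate", again on the condition that the share with "at least one moderate/severe COPD exacerbation after 1 year in the Tio 5 arm is 0.65".

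The visible text gives no source for 0.65 and does not relate it to the rate of 0.85.

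**The concern.** The two calculations describe the same event, in the same arm, over the same year. Once a negative binomial mean and dispersion are fixed, so is the share of patients with no event. The event share is therefore not a free input to the second calculation, and 0.65 looks too high for a mean of 0.85 with overdispersion.

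The number of events drives log-rank power, so an overstated event share overstates power. The endpoint is the second step of the confirmatory hierarchy (protocol section 7.2, SAP section 7.5.1). A reader of 7.6 would conclude that it has ample reserve, since the stated requirement is almost 1000 patients per arm below the planned 3900.

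**Working it through.** **Inputs (all from protocol section 7.6).** Tio 5 rate 0.85 per year; rate ratio and hazard ratio 0.88; 12 months; two-sided alpha 0.01 (z = 2.576); 90% power (z = 1.282); dispersion k = 0.625, 0.7, 0.8, 0.9; 3900 per arm; 15% loss of patient-years; Tio 5 event share 0.65.

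**1. Reproduce the key secondary figures.** Freedman's formula gives the events required:

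d = (2.576 + 1.282)² × [(1 + 0.88)/(1 − 0.88)]² = 3652.

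With p1 = 0.65, p2 = 1 − 0.35^0.88 = 0.603. N per arm = 3652/(0.65 + 0.603) = 2914.6, which matches 2915. At 3900 per arm, events = 3900 × 1.253 = 4887. Power = Φ(√4887 × 0.12/1.88 − 2.576) = 97.0%, which matches 97%.

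**2. Establish what the dispersion parameter means.** With variance μ + kμ²,

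N = (2.576 + 1.282)² × [(1/0.85 + 1/0.748) + 2k]/(ln 0.88)²

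gives 3426.7, 3563.3, 3745.4 and 3927.5, which match the table.

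**3. Establish how the 15% loss is applied.** Setting exposure to 0.85 year per patient in the same formula gives 85.8, 86.0, 86.2 and 86.4% at the table's sample sizes, and 90.6% down to 86.1% at 3900 per arm. All agree with the protocol. Cutting N by 15% instead would give 83.7% in every row, which does not.

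**4. Event share implied by the primary model.** P(at least one event in a year) = 1 − (1 + 0.85k)^(−1/k). The Poisson limit is 1 − e^(−0.85) = 57.3%. A share of 65% needs a yearly rate of (0.35^(−k) − 1)/k, or −ln 0.35 = 1.05 under Poisson.

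**5. Power at HR 0.88 with only the event share changed.** Here p2 = 1 − (1 − p1)^0.88, and the Freedman formula is as in step 1. The last row uses 0.85 year of follow-up, so p1 = 1 − (1 + 0.85 × 0.85k)^(−1/k) = 0.449, 0.443, 0.435, 0.427.

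| | k = 0.625 | 0.7 | 0.8 | 0.9 |
|---|---|---|---|---|
| Implied Tio 5 event share | 49.4% | 48.7% | 47.7% | 46.8% |
| Yearly rate needed for 65% | 1.48 | 1.55 | 1.65 | 1.75 |
| Events at 3900 per arm (stated inputs: 4887) | 3687 | 3630 | 3557 | 3488 |
| Power at 3900 per arm (stated: 97%) | 90.3% | 89.8% | 89.1% | 88.4% |
| N per arm for 90% power (stated: 2915) | 3863 | 3924 | 4004 | 4084 |
| Power with 0.85 year of follow-up | 86.8% | 86.2% | 85.4% | 84.6% |

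Log-rank simulation under proportional hazards (10,000 runs per cell) gives 90.6, 89.7, 88.9 and 88.4% without loss, and 86.8, 86.4, 85.7 and 84.8% with it. If the loss were taken as 15% fewer events, power would be 84.1% down to 81.6%.

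**6. Sensitivity analysis: hazard ratio taken from the same model.** If counts are negative binomial in both arms with rate ratio 0.88, survival to first event is S(t) = (1 + k·r·t)^(−1/k) with r = 0.85 and 0.748. The one-year cumulative hazard ratio, ln S₂(1)/ln S₁(1), is then 0.900, 0.902, 0.904 and 0.906. Simulated log-rank power at 3900 per arm is 76.5, 74.1, 70.3 and 67.6%, and with 0.85 year of follow-up 72.3, 70.7, 67.8 and 64.0%.

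A large-sample check uses hazards h = r/(1 + k·r·t), log-rank drift n∫S₁S₂(h₂ − h₁)/(S₁ + S₂)dt and variance n∫S₁S₂(S₁h₁ + S₂h₂)/(S₁ + S₂)²dt. It gives 75.7, 73.2, 69.9 and 66.7%, and 72.6, 70.2, 67.1 and 64.2%. The two methods agree to within about a point.

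**The case against.** - **The protocol's arithmetic is correct, and the documents do not show which input is weaker.** This stands. If 65% is the believed figure, 97% stands too, and the rate is what must change. At 1.48 to 1.75 events per year, the step 2 formula gives about 2450 (k = 0.625) to 2750 (k = 0.9) per arm for the primary endpoint, so the trial would be better powered on both endpoints. That is a legitimate resolution, but section 7.6 does not make it.
- **A mean of 0.85 and a 65% event share are not logically incompatible.** For instance, 35% of patients with no event, 61% with one and 4% with six gives mean 0.85, variance 1.33 and moment dispersion of about 0.66. This is true, but the distribution is contrived and is not the negative binomial on which Table 7.6:1 rests. Letting patients' Poisson rates vary only increases the share with no event, so 57.3% is the ceiling for any mixed-Poisson model with mean 0.85.
- **Restating power at HR 0.88 still mixes two models.** This stands: a rate ratio of 0.88 under the negative binomial gives a hazard ratio of about 0.90. The main restatement keeps the protocol's stated hazard ratio so that only one input changes. The model-consistent figure is kept apart as a sensitivity analysis.
- **The protocol never says the 15% loss applies to this endpoint.** Correct, and leaving it out is not a contradiction. It is relevant, however, because SAP section 7.5.1 censors patients one day after they stop medication early.
- **The effect is small.** At 88–90%, power is close to the 90% target and to the primary endpoint's own loss-adjusted range. The adequacy claim is expressly conditional on 0.65 and is tested only after the primary succeeds. This limits the consequence but does not make 97% consistent with the section's other inputs.

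**Conclusion.** The concern holds. The 0.65 is incompatible with the negative binomial model used for the same arm, event and year in the same section. With that model's event share and the stated hazard ratio of 0.88, the marginal power of the key secondary test at 3900 per arm is 88–90%. The chance of missing a true effect is therefore about 10–12% rather than 3%, or 13–15% with 0.85 year of follow-up. The apparent reserve over 2915 per arm disappears: 3900 reaches 90% only at dispersion 0.625, and narrowly misses it at 0.7.

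These figures rest on the 0.85 rate and the table's dispersions being the inputs to keep, on proportional hazards, and on full 12-month follow-up unless the loss is stated. They are marginal figures, not the probability of success through the hierarchy. The choice of 7800 patients, made for the primary endpoint, and the type I error control are not affected.

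**What to change.** Keep 7800 patients. In section 7.6, base both calculations on one event model, by one of two routes:

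1. **Keep 0.85 per year and the table's dispersions.** Replace 0.65 with the implied 47–49%. State 3863–4084 per arm for 90% power at HR 0.88, and power at 3900 per arm of about 88–90%, or about 85–87% with the 15% loss. Say that the loss is applied as 0.85 year of follow-up per patient, as in the primary calculation. Add, labelled as a sensitivity analysis, the power when the hazard ratio comes from the same model: roughly 67–76% before loss.
2. **Keep 65%, if that is the believed figure.** Give its source, revise the annual rate to match and redo Table 7.6:1.

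Under the first route, qualify the closing statement on adequate power with these figures. The cost is a rewording of section 7.6 and, on that route, a less favourable stated power for the key secondary endpoint. No patients are added, and alpha, analysis and conduct do not change.
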